**Diagnostic Assessments:**

13. A positive urine drug test at Screening or on Day -1.

**NOTE:** Participants in Cohort 2 who have been medically prescribed opiates/opioids or benzodiazepines and report the use of these drugs to the investigator at Screening may be allowed to participate if approved by the sponsor.

14. In females of childbearing potential, a positive urine pregnancy test at Screening or Day -1.

15. Vital sign measurements at Screening that demonstrates:

**[For Cohort 1 only]** Screening seated BP  $\geq 140$  mm Hg (systolic) or  $\geq 90$  mm Hg (diastolic), following at least 5 minutes of rest.

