**[For Cohort 2 only]**

- Screening seated BP  $\geq 180$  mm Hg and/or  $\geq 100$  mm Hg (diastolic) following at least 5 minutes of rest.

**NOTE:** If SBP is  $\geq 140$  mm Hg (for Cohort 1) **or**  $\geq 180$  mm Hg (for Cohort 2) or if DBP  $\geq 90$  mm Hg (for Cohort 1) or  $\geq 100$  mm Hg (for Cohort 2), the BP should be repeated 2 more times and the average of the 3 BP values should be used to determine the participant's eligibility.

- For participants with SBP  $\geq 160$  (and  $<180$ ) mm Hg **or** DBP  $\geq 95$  (and  $<100$ ) mm Hg, the period between Screening and Day -1 must be used to refine the doses of the agents used for management of BP with the aim to have stable BP by Day -1. Participants must have measurement on Day 1 of SBP  $\leq 160$  mm Hg **and** DBP  $<95$  mm Hg.

16. Screening standard 12-lead ECG that demonstrates:

- Clinically relevant abnormalities requiring treatment (eg, acute myocardial infarction, serious tachy- or brady-arrhythmias) or indicating serious underlying heart disease (eg, prolonged PR interval, cardiomyopathy, underlying structural heart disease, Wolff Parkinson-White syndrome);

**[For Cohort 1 only]** Screening supine 12-lead ECG demonstrating QTcF interval  $>450$  msec or a QRS interval  $>120$  msec;

**[For Cohort 2 only]** Screening supine 12-lead ECG demonstrating a QTcF interval  $>470$  msec or a QRS interval  $>120$  msec;

**NOTE:** If QTcF exceeds 450 msec (for Cohort 1) or 480 msec (for Cohort 2), **or** QRS exceeds 120 msec, the ECG should be repeated 2 more times and the average of the 3 QTcF or QRS values should be used to determine eligibility.

17. Participants with **ANY** of the following abnormalities in clinical laboratory tests at screening, as assessed by the study -specific laboratory and confirmed by a single repeat test, if deemed necessary:

- eGFR <60 mL/min/1.73m^2 based on the CKD-EPI equation, with single repeat allowed.
- **[For Cohort 1 only]**
  - AST **or** ALT level  $\geq$  ULN;
  - Albumin > ULN;
  - Prothrombin time > ULN;
  - Total bilirubin level  $\geq 1.5 \times$  ULN;

**NOTE:** Participants with a history of Gilbert syndrome (and hence elevated total bilirubin) are eligible provided direct bilirubin level is  $\leq$  ULN;

- **[For Cohort 2 only]** ALT **or** AST  $>5 \times$  ULN

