#### **5.4. Screen Failures**

Screen failures are defined as participants who consent to participate in the clinical study but are not subsequently enrolled in the study. Screen failure data are collected and remain as source and are not reported to the clinical database.

Individuals who do not meet the criteria for participation in this study (screen failure) may be rescreened if prior reason for not meeting the eligibility criteria has been resolved. Rescreening may only occur with sponsor approval. In the event that the participation of a participant in the study is delayed, outdated screening procedures can be repeated. Rescreened participants should be assigned the same participant number as for the initial screening.

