### 8.2.3. Electrocardiograms

Standard 12-lead ECGs utilizing limb leads (with a 10 second rhythm strip) should be collected at times specified in the **SoA** section of this protocol using an ECG machine that automatically calculates the heart rate and measures PR, QT, and QTc intervals and QRS complex. Alternative lead placement methodology using torso leads (eg, Mason-Likar) should not be used given the potential risk of discrepancies with ECGs acquired using standard limb lead placement. All scheduled ECGs should be performed after the participant has rested quietly for at least 5 minutes in a supine position.

To ensure safety of the participants, a qualified individual at the investigator site will make comparisons to baseline measurements. Additional ECG monitoring will occur if a) a postdose QTcF interval is increased by  $\geq 30$  msec from the baseline **and** is  $> 450$  msec for participants with normal hepatic function and  $> 470$  msec for participants with impaired hepatic function; or b) an absolute QT value is  $\geq 500$  msec for any scheduled ECG. If either of these conditions occurs, then 2 additional ECGs will be collected approximately 2 to 4 minutes apart to confirm the original measurement. If the QTc values from these repeated ECGs remain above the threshold value, then a single ECG must be repeated at least hourly until QTc values from 2 successive ECGs fall below the threshold value that triggered the repeat measurement.

If a) a postdose QTcF interval remains  $\geq 30$  msec from the baseline **and** is  $> 450$  msec for participants with normal hepatic function and  $> 470$  msec for participants with impaired hepatic function; or b) an absolute QT value is  $\geq 500$  msec for any scheduled ECG for greater than 4 hours (or sooner, at the discretion of the investigator); or c) QTcF intervals get progressively longer, the participant should undergo continuous ECG monitoring.

A cardiologist should be consulted if QTcF intervals do not return to less than the criteria listed above after 8 hours of monitoring (or sooner, at the discretion of the investigator).

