## 10.7. Appendix 7: ECG Findings of Potential Clinical Concern

ECG Findings That May Qualify as AEs

Marked sinus bradycardia (rate <40 bpm) lasting minutes.

New PR interval prolongation >280 msec.

New prolongation of QTcF to >480 msec (absolute) or by <math>\geq</math>60 msec from baseline.

New-onset atrial flutter or fibrillation, with controlled ventricular response rate: ie, rate <120 bpm.

New-onset type I second-degree (Wenckebach) AV block of >30 seconds' duration.

Frequent PVCs, triplets, or short intervals (<30 seconds) of consecutive ventricular complexes.

ECG Findings That May Qualify as SAEs

QTcF prolongation >500 msec.

New ST-T changes suggestive of myocardial ischemia.

New-onset left bundle branch block (QRS >120 msec).

New-onset right bundle branch block (QRS >120 msec).

Symptomatic bradycardia.

Asystole:

In awake, symptom-free participants in sinus rhythm, with documented periods of asystole <math>\geq</math>3.0 seconds or any escape rate <40 bpm, or with an escape rhythm that is below the AV node.

In awake, symptom-free participants with atrial fibrillation and bradycardia with 1 or more pauses of at least 5 seconds or longer.

Atrial flutter or fibrillation, with rapid ventricular response rate: rapid = rate >120 bpm.

Sustained supraventricular tachycardia (rate >120 bpm) ("sustained" = short duration with relevant symptoms or lasting >1 minute).

[figure not shown]
[figure not shown]
- Ventricular rhythms >30 seconds' duration, including idioventricular rhythm (heart rate <40 bpm), accelerated idioventricular rhythm (HR >40 bpm to <100 bpm), and monomorphic/polymorphic ventricular tachycardia (HR >100 bpm (such as torsades de pointes)).
- Type II second-degree (Mobitz II) AV block.
- Complete (third-degree) heart block.

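### In criterion 16 the Cohort 2 QTcF limit (470 msec) and the trigger for repeat ECGs (480 msec) do not match, so a first reading above 470 and up to 480 msec with QRS of 120 msec or less excludes on a single ECG

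*Protocol*

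**What the plan says.** Protocol Section 5.2, criterion 16, sets the Cohort 2 exclusion as "Screening supine 12-lead ECG demonstrating a QTcF interval" above 470 msec, or QRS above 120 msec. For Cohort 1 the limits are 450 and 120 msec.

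The NOTE under the same criterion says when a reading is to be confirmed: "If QTcF exceeds 450 msec (for Cohort 1) or 480 msec (for Cohort 2"), or if QRS is above 120 msec. In those cases "the ECG should be repeated 2 more times and the average of the 3 QTcF or QRS values should be used to determine eligibility".

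Criterion 15 handles blood pressure in the same way. A reading at or above the limit means that "the BP should be repeated 2 more times and the average of the 3 BP values should be used to determine" eligibility. There the repeat triggers equal the exclusion limits in both cohorts.

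The Schedule of Activities plans a single supine ECG at Screening. Section 5 does not permit eligibility waivers.

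**The concern.** A repeat-and-average rule protects a candidate from exclusion on one unrepresentative reading. To do that, it has to start at the exclusion limit. For Cohort 2 QTcF it starts 10 msec above the limit, so the candidates closest to the limit, for whom a repeat is most likely to change the decision, do not get one. A candidate further above the limit does.

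What is at stake is consistent eligibility decisions for a cohort of 8. Some candidates could be turned away without the confirmation that others receive. The analysis of participants who are enrolled does not depend on this rule.

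**Working it through.** **Step 1. Compare every limit with its repeat trigger (criteria 15 and 16).**

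| Parameter | Cohort | Exclusion limit | Repeat trigger | Gap |
|---|---|---|---|---|
| SBP, mm Hg | 1 | 140 | 140 | 0 |
| SBP, mm Hg | 2 | 180 | 180 | 0 |
| DBP, mm Hg | 1 | 90 | 90 | 0 |
| DBP, mm Hg | 2 | 100 | 100 | 0 |
| QTcF, msec | 1 | 450 | 450 | 0 |
| QTcF, msec | 2 | 470 | 480 | **10** |
| QRS, msec | 1 | 120 | 120 | 0 |
| QRS, msec | 2 | 120 | 120 | 0 |

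Seven of eight pairs match. The Cohort 2 blood pressure adjustment band and its Day 1 check are a different rule and are not counted.

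**Step 2. Apply the text to example readings (illustrative, QRS 120 msec or less).**

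- First QTcF 475: above 470, so the exclusion is met. It is not above 480, so no repeat is called for and the candidate is excluded on one ECG. Had repeats of 462 and 460 been taken, the mean would be (475 + 462 + 460)/3 = 465.7, within the limit.
- First QTcF 485 with the same repeats: (485 + 462 + 460)/3 = 469.0. The candidate is eligible.
- First QTcF 475 with QRS above 120: the QRS trigger applies, so repeats are taken. The gap therefore needs QRS of 120 or less.

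**Step 3. Which number is likely wrong.** Section 8.2.3 uses 450 msec for normal and 470 msec for impaired hepatic function, the same two figures as the limits in criterion 16. That points to 480 as the error. It is not proof: Section 8.2.3 is a post-dose rule, and Appendix 7 lists "New prolongation of QTcF to" above 480 msec among findings that may qualify as AEs.

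**Step 4. How often it could matter (assumptions only).** The documents give no QTcF distribution. Assume normal readings X1, X2, X3 with mean M, variance v and pairwise correlation r. The event of interest is 470 < X1 ≤ 480 with a three-reading mean of 470 or less, that is X2 + X3 ≤ 1410 − X1. Given X1 = x, X2 + X3 is normal with mean 2M + 2r(x − M) and variance v[2(1 + r) − 4r²]. Integrate over x from 470 to 480.

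*For one candidate with a fixed true QTcF*, within-person SD 10 msec, v = 100 and r = ρ:

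| True QTcF | ρ = 0 | ρ = 0.5 | ρ = 0.8 |
|---|---|---|---|
| 450 | 2.1% | 1.8% | 1.1% |
| 455 | 5.9% | 4.3% | 2.5% |
| 460 | 11.8% | 7.6% | 4.4% |
| 465 | 15.9% | 10.0% | 5.9% |

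The reversal in Step 2 (first reading above 480, mean 470 or less) is rarer. Across true QTcF 450 to 465 it is 0.13 to 2.6% at ρ = 0, 0.05 to 0.44% at 0.5, and 0.002 to 0.013% at 0.8.

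*Across all candidates*, with true QTcF mean M of 420 to 440, between-person SD B of 15 to 20, within-person SD s of 8 to 12, and ρ of 0 to 0.8: v = B² + s² and r = (B² + ρs²)/v.

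- Lowest (M 420, B 15, s 8, ρ 0.8): v = 225 + 64 = 289 and r = 276.2/289 = 0.956. The probability is 0.05%.
- Highest (M 440, B 20, s 12, ρ 0): v = 400 + 144 = 544 and r = 400/544 = 0.735. The probability is 3.2%.

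If 20 candidates were screened (also assumed), the expected number is 20 × 0.0005 = 0.01 to 20 × 0.032 = 0.64. At the top of the range, the chance that nobody is affected is (1 − 0.032)^20, or about 52%.

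**The case against.** The strongest reply is that this is one number in a NOTE with a conservative effect. Judged against the 470 msec limit, the mismatch withholds a confirmatory average but admits nobody whose average is above 470. Section 5.4 lets a failed candidate be rescreened if the reason has resolved ("Rescreening may only occur with sponsor approval"), and Section 8.2.3 allows abnormal ECGs to be repeated when lead placement is in doubt. Most of this stands, and it is why the point is minor. Neither provision supplies the three-reading average for eligibility, so neither closes the gap.

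Three stronger readings are tempting, and the documents do not support them.

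- *Every Cohort 2 reading above 470 and up to 480 goes without a repeat.* This is too broad, because QRS above 120 msec also triggers repeats and averaging.
- *The average has no stated limit, so a site could judge it against 480 and admit, say, 485/475/470 with a mean of 476.7.* The NOTE sits directly under the only Cohort 2 eligibility limit, which is 470. The blood pressure NOTE has the same form without causing difficulty. Applying 480 to the average would mean replacing a stated limit with a repeat trigger.
- *Worse first readings will regularly be let in ahead of milder ones.* The reversal is possible, but the example needs falls of 23 and 25 msec between readings. It is rare if repeats are strongly correlated.

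**Conclusion.** The mismatch is real. For Cohort 2 with QRS of 120 msec or less, a first QTcF above 470 and up to 480 msec excludes on a single ECG, while a higher first reading is averaged. It is the only unmatched pair of the eight in criteria 15 and 16, and 480 is probably, though not certainly, the wrong figure.

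The only size that rests on the documents is the 10 msec gap. The estimate of about 0.05 to 3.2% of candidates depends wholly on the assumed QTcF means, SDs and correlations. The number affected is unknown and most likely zero.

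Severity is minor. A reader might infer a threat to the primary comparison, but the rule acts only at screening. The ANOVA and its 90% confidence intervals for AUC and Cmax are unchanged.

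**What to change.** In the criterion 16 NOTE, change the Cohort 2 repeat trigger from 480 to 470 msec. The gap then falls from 10 msec to 0, and all eight pairs match. A sentence confirming that each cohort's QTcF limit (450 msec for Cohort 1, 470 msec for Cohort 2) applies to the average of the three readings is optional. Section 8.2.3 and Appendix 7 need no change.

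If the sponsor did intend 480 msec, the exclusion limit would have to change instead. That would be a clinical decision to widen eligibility, and nothing in the documents argues for it.

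The cost is one number in the text and a few extra repeat ECGs at Screening for Cohort 2 candidates who first read above 470 and up to 480 msec.

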#### **Other Exclusions:**

19. History of alcohol abuse or binge drinking and/or any other illicit drug use or dependence within 6 months of Screening. Binge drinking is defined as a pattern of 5 (male) and 4 (female) or more alcoholic drinks in about 2 hours. As a general rule, alcohol intake should not exceed 14 units per week (1 unit = 8 ounces (240 mL) beer, 1 ounce (30 mL) of 40% spirit or 3 ounces (90 mL) of wine).

- At Screening or Day -1, a positive breath alcohol test or urine test.

20. Female participants of childbearing potential who are unwilling or unable to use highly effective methods of contraception as outlined in [Section 5.3.4](#) for the duration of the study and for at least 28 days after the administration of investigational product, pregnant female participants, female participants planning to become pregnant during the duration of the study until 28 days after the administration of investigational product, breastfeeding female participants.

21. Blood donation (excluding plasma donations) of approximately 1 pint (500 mL) or more within 60 days prior to dosing.

22. History of sensitivity reactions to ritonavir, or any of the formulation components of PF-07321332 or ritonavir.
23. History of sensitivity to heparin or heparin induced thrombocytopenia, only if heparin is used to flush intravenous catheters used during serial blood collections.
24. Unwilling or unable to comply with the criteria in the Lifestyle Considerations section of this protocol.
25. Investigator site staff or Pfizer employees directly involved in the conduct of the study, site staff otherwise supervised by the investigator, and their respective family members.

### **5.3. Lifestyle Considerations**

The following guidelines are provided:

#### **5.3.1. Meals and Dietary Restrictions**

- Participants must abstain from all food and drink (except water) at least 4 hours prior to any safety laboratory evaluations and overnight (at least 6 hours) prior to the collection of the predose PK sample and PF-07321332 administration on Day 1. There will be no restriction to breakfast on the other days provided other restrictions are followed.
- Water is permitted until 1 hour prior to study intervention administration. Water may be consumed without restriction beginning 1 hour after dosing. Noncaffeinated drinks (except grapefruit or grapefruit related citrus fruit juices - see below) may be consumed with meals and the evening snack.
- Participants will refrain from consuming red wine, grapefruit, or grapefruit-related citrus fruits (eg, Seville oranges, pomelos) from 7 days prior to the first dose of study intervention until collection of the final PK blood sample.
- While participants are confined, their total daily nutritional composition should be approximately 55% carbohydrate, 30% fat, and 15% protein. The daily caloric intake per participant should not exceed approximately 3200 kcal.

#### **5.3.2. Caffeine, Alcohol, and Tobacco**

- Consumption of caffeinated drinks and tobacco (or nicotine containing products) is permitted during participation in the study; however, there may be a need for brief interruption while at the site, depending on local site policy.

#### **5.3.3. Activity**

- Participants will abstain from strenuous exercise (eg, heavy lifting, weight training, calisthenics, aerobics) for at least 48 hours prior to each blood collection for clinical laboratory tests. Walking at a normal pace will be permitted.

- In order to standardize the conditions on PK sampling days, participants will be required to refrain from lying down (except when required for BP, pulse rate, and ECG measurements), eating, and drinking beverages other than water during the first 4 hours after dosing of PF-07321332 (does not apply to ritonavir dosing).

#### **5.3.4. Contraception**

The investigator or his or her designee, in consultation with the participant, will confirm that the participant has selected an appropriate method of contraception for the individual participant and his or her partner(s) from the permitted list of contraception methods (see [Appendix 4 Section 10.4.4](#)) and will confirm that the participant has been instructed in its consistent and correct use. At time points indicated in the schedule of activities ([SoA](#)), the investigator or designee will inform the participant of the need to use highly effective contraception consistently and correctly and document the conversation and the participant's affirmation in the participant's chart (participants need to affirm their consistent and correct use of at least 1 of the selected methods of contraception) considering that their risk for pregnancy may have changed since the last visit. In addition, the investigator or designee will instruct the participant to call immediately if the selected contraception method is discontinued or if pregnancy is known or suspected in the participant or partner.

#### **5.4. Screen Failures**

Screen failures are defined as participants who consent to participate in the clinical study but are not subsequently enrolled in the study. Screen failure data are collected and remain as source and are not reported to the clinical database.

Individuals who do not meet the criteria for participation in this study (screen failure) may be rescreened if prior reason for not meeting the eligibility criteria has been resolved. Rescreening may only occur with sponsor approval. In the event that the participation of a participant in the study is delayed, outdated screening procedures can be repeated. Rescreened participants should be assigned the same participant number as for the initial screening.

### **6. STUDY INTERVENTION(S) AND CONCOMITANT THERAPY**

Study intervention is defined as any investigational intervention(s), marketed product(s), placebo, medical device(s), or study procedure(s) intended to be administered to a study participant according to the study protocol.

For the purposes of this protocol, study intervention refers to PF-07321332 and ritonavir.

#### **6.1. Study Intervention(s) Administered**

For this study, the investigational products are PF-07321332 (provided as 100 mg tablets) and ritonavir (provided as 100 mg tablets).

PF-07321332 100 mg tablets and ritonavir 100 mg tablets will be supplied by Pfizer to the CRU in bulk along with individual dosing containers for unit dosing.

### **6.1.1. Administration**

Investigational products will be administered orally and according to the conditions described in the [SoA](#) section and Protocol [Section 5.3.1](#) Meals and Dietary Restrictions.

On Day -1, 12 hours prior to dosing of PF-07321332, participants will receive a 100 mg ritonavir tablet (as 1 × 100 mg) with approximately 240 mL ambient temperature water. On Day 1, following an overnight fast of at least 6 hours, participants will receive 100 mg PF-07321332 (as 1 × 100 mg tablet) at approximately 0800 hours (plus or minus 2 hours) and 100 mg ritonavir (as 1 × 100 mg tablet). Participants will receive 2 additional doses of 100 mg ritonavir (as 1 × 100 mg tablet) at 12 and 24 hours after receiving PF-07321332. Investigator site personnel will administer study intervention with ambient temperature water to a total volume of approximately 240 mL. Participants will swallow the study intervention whole and will not manipulate or chew the study intervention prior to swallowing.

In order to standardize the conditions of PK sampling, all participants will be required to refrain from lying down (except when required for ECG measurements), eating, and drinking beverages other than water during the first 4 hours after dosing of PF-07321332.

### **6.2. Preparation, Handling, Storage, and Accountability**

1. The investigator or designee must confirm appropriate temperature conditions have been maintained during transit for all study interventions received and any discrepancies are reported and resolved before use of the study intervention.
2. Only participants enrolled in the study may receive study intervention and only authorized site staff may supply or administer study intervention. All study interventions must be stored in a secure, environmentally controlled, and monitored (manual or automated recording) area in accordance with the labeled storage conditions with access limited to the investigator and authorized site staff. At a minimum, daily minimum and maximum temperatures for all site storage locations must be documented and available upon request. Data for nonworking days must indicate the minimum and maximum temperatures since previously documented for all site storage locations upon return to business.
3. Any excursions from the study intervention label storage conditions should be reported to Pfizer upon discovery along with any actions taken. The site should actively pursue options for returning the study intervention to the storage conditions described in the labeling, as soon as possible. Once an excursion is identified, the study intervention must be quarantined and not used until Pfizer provides permission to use the study intervention. Specific details regarding the definition of an excursion and information the site should report for each excursion will be provided to the site in the IP manual.
4. Any storage conditions stated in the SRSD will be superseded by the storage conditions stated on the label.
5. Study interventions should be stored in their original containers.

PFIZER CONFIDENTIAL

6. The investigator, institution, or the head of the medical institution (where applicable) is responsible for study intervention accountability, reconciliation, and record maintenance (ie, receipt, reconciliation, and final disposition records), such as the IPAL or sponsor-approved equivalent. All study interventions will be accounted for using a study intervention accountability form/record.
7. Further guidance and information for the final disposition of unused study interventions are provided in the IP manual. All destruction must be adequately documented. If destruction is authorized to take place at the investigator site, the investigator must ensure that the materials are destroyed in compliance with applicable environmental regulations, institutional policy, and any special instructions provided by Pfizer.

Upon identification of a product complaint, notify the sponsor within 1 business day of discovery as described in the IP manual.

